#### **Visit 5** (End of Treatment or Early Termination of Treatment)

- Laboratory (chemistry, hematology, coagulation and urinalysis per Section 5.2);
- 12 lead-ECG;
- Vitals;
- Respiratory assessments per Section 5.3;
- SBT and at any time that weaning criteria is met;
- OSCi assessment;
- AEs;
- Concomitant medications.

#### **Days 7, 9, 12 and 14**

- Laboratory (chemistry, hematology and coagulation per Section 5.2) (Day 14);
- 12 lead-ECG (Days 7, 9, 14);
- Vitals;
- Respiratory assessments per Section 5.3;
- SBT at Days 7, 9 and 14 and at any time that weaning criteria is met;
- AEs;
- Concomitant medications.

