#### 2.1.1 Primary Objectives and Endpoints

The primary objectives of safety and tolerability of USB002 will be evaluated for rate of occurrence and severity of AEs resulting from clinical changes (Visit 1/Day 1 to Day 28): cardiovascular parameters, to include blood pressure (BP), heart rate (HR), 12-lead electrocardiogram (ECG), and requirements for inotropes and vasopressors; laboratory parameters, to include kidney and liver function.

The primary endpoint of preliminary efficacy will be demonstrating the difference between USB002 and placebo groups in time to peripheral capillary oxygen saturation ( $\text{SpO}_2$ )  $\geq 94\%$ , sustained for at least 48 hours, on room air through Day 28.

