Visit 5 will serve as the End of Treatment visit for Part 1. Additional visits will be conducted on Days 7, 9, 12, 14, 16, 18, 21, 24 and 28 (if/while still hospitalized). The follow-up visits on Days 28 and 60 will be conducted by phone (Telemed) upon discharge. If the subject is discharged earlier than Day 28, Telemed visits will be conducted once a week until Day 28, with the first occurring 7 days after discharge. The Day 28 Telemed visit and Day 60 Telemed visit will occur on Days 28 and 60, respectively, regardless of when the subject is discharged from hospital and the timing of their previous weekly Telemed visits.

The decision to dose-escalate, de-escalate, or increase the number of subjects in any group will be made by a Data Safety Monitoring Board (DSMB) as described in Section 6.6. Dose escalation will use the traditional 3+3 design to assess dose-response as described in Section 3.2. Assessment of progress and safety will be conducted by the DSMB, per the Safety Management Plan (SMP). If the DSMB determines there is a reasonable safety concern, enrollment may be delayed or halted. If toxicity is identified (graded according to NCI-CTCAE v5.0) at the lowest cohort level (90 ug/kg/day), DSMB may determine to de-escalate or halt the study. Escalation will continue until Part 1 enrollment is completed and the MTD is determined.

## Part 2

30 subjects will be randomized at the MTD, as determined in Part 1, to either SOC plus USB002 (n=15) or SOC plus placebo (n=15). Subjects will be treated on a continuous infusion for up to 14 days. Infusion will be discontinued at any time if  $\text{SpO}_2 \geq 94\%$  on room air is sustained for at least 48 hours. Additional visits will be conducted on Days 16 (End of Treatment visit), 18, 21, 24 and 28 (if still hospitalized). The follow-up visit on Days 28 and 60 will be conducted by phone (Telemed) upon discharge. If the subject is discharged earlier than Day 28, Telemed visits will be conducted once a week until Day 28, with the first occurring 7 days after discharge. The Day 28 Telemed visit and Day 60 Telemed visit will occur on Days 28 and 60, respectively, regardless of when the subject is discharged from hospital and the timing of their previous weekly Telemed visits.

## Parts 1 and 2

For both groups, there will be a 24-hour observation period, after infusion stop time, regardless of when this occurs and regardless of reason.

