### 5.3 Other Assays or Procedures

Other assays or procedures include:

- Pregnancy test (for females of childbearing potential).
- OSCI (Appendix 1);
  - In addition to study required OSCI status collection, any additional OSCI assessments conducted during the study will also be collected.
- SBT (Appendix 2);
- Chest X-ray (required at screening only);

- 12-lead ECG to include HR and QRS intervals, QT/QTcF/QTcB; Correlation of QT values using Fridericia's formula;
- Vitals to be captured daily; and during the infusion period at a minimum of every 8 hours. Vitals to include systolic and diastolic BP, HR, RR and temperature;
  - If BP changes significantly post start of infusion, mean arterial pressure will be collected at 15-minute intervals, until resolution;
- Weight measured at screening only;
- Study-required respiratory assessments (first and last assessments can be based on 24 hour clock or from infusion time):
  - Arterial Blood Gas (ABG): If multiple assessments are conducted daily, the first and last assessment of the day will be collected; missed ABGs do not qualify as deviations,
  - $\text{FiO}_2$  (%) – The highest value in a 24-hour period to be recorded in the event of multiple daily assessments,
  - $\text{PaO}_2/\text{FiO}_2$  ratio, the  $\text{PaO}_2$  value to be obtained from the ABG when performed,
  - Respiratory rate (breaths/min) – The highest value in a 24-hour period to be recorded in the event of multiple daily assessments,
  - $\text{SpO}_2$  (%) – The lowest value in a 24-hour period to be recorded in the event of multiple daily assessments.

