#### **Day 16**

- Vitals;
- Respiratory assessments per Section 5.3;
- SBT and at any time that weaning criteria is met;
- OSCi assessment;
- AEs;
- Concomitant medications.

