### **5.4.3. Visit Schedule Part 2**

AEs and concomitant medications will be reviewed and documented every day of hospitalization. Monitoring is to be conducted daily if no continuous monitoring is available, unless specified below.

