## 11.2 Source Documents

An eCRF is required and must be completed for each consenting and enrolled subject by qualified and authorized personnel. Any correction to eCRF entries must be reflected in a validated audit trail. Only data required by the protocol for the purposes of the study should be collected within the EDC. The Investigator must maintain adequate and accurate source documents on which the eCRFs for each subject are based. They will be separate and distinct from the eCRFs. These records should include detailed notes on:

- The medical history prior to the subject's involvement in the study;
- Date of informed consent;
- Basic identifying information that links the subject medical record with the eCRFs;
- Screening, enrollment, treatment visits, End of Treatment and follow-up visit details including dates and reasons for early termination;
- Results of all diagnostic tests performed, diagnoses made, therapy provided, and any other data on the condition of the subject;
- All AEs;
- The subject's exposure to the study medication;
- The subject's exposure to any concomitant therapy;
- All relevant observations and data on the condition of the subject throughout the trial;
- Justification for all entries in the subject's eCRF.

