4.2. Primary Endpoints

The primary endpoint of the study will be safety and tolerability, as demonstrated by adverse events (AE), changes in laboratory assessments, ECG assessments, vital signs, and concomitant medications (inotropes and vasopressors).

The primary endpoint of preliminary efficacy will be demonstrating the difference between USB002 and placebo groups in time to peripheral capillary oxygen saturation (SpO_2) $\geq 94\%$ on room air, sustained for at least 48 hours, through Day 28.

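### After Visit 5, Part 1 schedules SpO2 only on Days 7, 9, 12, 14 and 16, so the 48-hour condition of the co-primary efficacy endpoint cannot be verified for many inpatient recoveries.

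*Protocol*

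**What the plan says.** Protocol Section 2.1.1 defines the efficacy endpoint as time to SpO2 of at least 94%, "sustained for at least 48 hours, on room air through Day 28". SAP Section 4.2 has the same condition ("on room air, sustained for at least 48 hours, through Day 28"), and SAP Section 8.2 calls the endpoint co-primary.

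Protocol Section 5.3 places SpO2 among the respiratory assessments and records one value per 24 hours, the lowest. Section 3 sets the later Part 1 visits: "Additional visits will be conducted on Days 7, 9, 12, 14, 16, 18, 21, 24 and 28 (if/while still hospitalized"). Within that calendar, Section 5.4.2 lists respiratory assessments under "Days 7, 9, 12 and 14" and again on Day 16 ("Respiratory assessments per Section 5.3"). The list for Days 18 to 28 has none.

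The Part 1 preamble to Section 5.4.2 makes only adverse events and concomitant medications a daily record. Section 5.3 has vital signs captured daily but defines them without SpO2: "Vitals to include systolic and diastolic BP, HR, RR and temperature". Section 7.2.3.3, on the analysis of vital signs, does name SpO2 among them. Section 11.2 adds: "Only data required by the protocol for the purposes of the study should be collected within the EDC".

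SAP Section 7.2 dates the event at the first SpO2 of at least 94% on room air, and Section 8.2.6 summarises that time. Neither applies the 48-hour condition.

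**The concern.** The endpoint describes a state that must hold for 48 hours, but the scheduled readings are themselves 48 or 72 hours apart. A run on room air that ends with discharge, or with a return to oxygen, may contain only one scheduled reading, and a short one between Days 9 and 12 may contain none. Even where two qualifying readings are 48 hours apart, as on Days 7 and 9, nothing need be recorded on the day between.

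This matters because Part 1 supplies all the data. SAP Section 2 reports 21 subjects, all in Part 1: three cohorts of 6 and one of 3. SAP Section 8.2.6 compares the arms within each cohort, where the design has at most 3 subjects per arm. One recovery that is wrongly counted, or misdated by a day or two, visibly changes such a summary.

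**Working it through.** The documents give no figure to reproduce, so the check is a count on the visit calendar.

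**Inputs**
- Reading days: 5, 7, 9, 12, 14 and 16. Day 5 is the 96-hour assessment (Day 1 plus 4 days), and Protocol Section 4.3 also places Part 1 End of Treatment on Day 5. The others come from Section 5.4.2.
- Gaps: 2, 2, 3, 2 and 2 days, which is 48, 48, 72, 48 and 48 hours.
- Discharged subjects do not return for scheduled procedures (Section 5.4.5), so discharge ends the series.
- Assumptions of this check, not in the documents: recovery day r is equally likely on Days 5 to 13, recovery persists to discharge on day r + L, and a reading on the day of discharge counts.

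**1. The SAP derivation as written (first qualifying reading).** With L = 2 or more, every r from 5 to 13 has at least one visit in [r, r + L], so 0 of 9 are lost. A single reading counts whether or not the state lasted.

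On whole days, the delay is the next reading day minus r. For r = 6 to 16 the delays are 1, 0, 1, 0, 2, 1, 0, 1, 0, 1 and 0. They sum to 7, so the mean is 7/11 = 0.64 day and the maximum is 2 days (r = 10). This average covers all recovery days, confirmable or not.

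With onset at any hour, the mean delay from Day 5 to Day 16 is (2² + 2² + 3² + 2² + 2²) / (2 × 11) = 25/22 = 1.1 days. The maximum is just under 3 days, for onset soon after the Day 9 reading.

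**2. The 48-hour condition enforced with two visit readings.** Confirmation needs two reading days in [r, r + L] at least 2 days apart.

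| Discharge after recovery | Recovery days that cannot be confirmed | Share |
|---|---|---|
| L = 2 days | 6, 8, 9, 10, 11, 13 | 6 of 9 (67%) |
| L = 3 days | 8, 10 | 2 of 9 (22%) |
| L = 4 days | none | 0 of 9 |

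Among the seven confirmable days at L = 3 (5, 6, 7, 9, 11, 12, 13), the delays are 0, 1, 0, 0, 1, 0 and 1: mean 3/7 = 0.43 day, maximum 1.

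**3. Sensitivity to whole-day counting.** Let onset fall evenly at any hour from Day 5 to Day 16 (11 days). Onset times that leave two readings 48 hours apart total 0 of 11 days for a 48-hour run. For a 72-hour run they total 1 + 1 + 1 = 3 of 11 (27%), and for a 96-hour run 2 + 1 + 2 + 2 = 7 of 11 (64%). This version is harsher, partly because it includes onsets after Day 14, which have no second reading.

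**4. Daily readings.** Any 48-hour run would hold at least two readings, and the dating delay would be under 1 day.

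**The case against.** Several objections carry weight.

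- A reader might infer that subjects who recovered in hospital will be recorded as not recovering. The SAP does not support that: its derivation needs one reading, and in the model above none is lost. The 67% and 22% apply only to a two-reading rule that neither document states. What stands is the opposite error, events counted without evidence of duration, plus late dates.
- A reader might infer that the protocol rules out daily SpO2. It does not do so clearly. Section 7.2.3.3 lists SpO2 with the vital signs, Section 5.3 makes vital signs daily, and SAP Section 8.2 intends to list SpO2 results to Day 28. Against this, Section 5.3's own definition of vital signs omits SpO2, and Section 7.2.3.3 refers to scheduled assessments. This is an inconsistency to reconcile.
- A reader might take Part 2 as a model that already provides daily SpO2, from Section 5.4.3: "Monitoring is to be conducted daily if no continuous monitoring is available, unless specified below". That sentence names neither SpO2 nor eCRF entry, and Protocol Table 3 has the same visit spacing from Day 5.
- Part 1 efficacy is descriptive, and SAP Section 7.4 plans no inference. Both blinded arms share the schedule, so nothing here shows a bias between them. This limits the consequence, but the endpoint still is not measured as defined.
- Recoveries during the infusion are read more densely (4 to 96 hours), and longer inpatient recoveries can be confirmed. Both points stand.

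**Conclusion.** The point holds in a limited form. The 48- to 72-hour gaps follow directly from the schedule. Because a daily SpO2 record is not clearly required, the sustained condition cannot be verified from scheduled data for many inpatient recoveries after Visit 5.

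Under the current SAP derivation, unsustained or unconfirmed recoveries count as events. Dates can be late by up to 2 days on whole-day counting, averaging about 0.6 day over recovery Days 6 to 16, or by just under 3 days between Days 9 and 12 with continuous onset. Under a two-reading rule, 6 of 9, 2 of 9 or 0 of 9 recovery days could not be confirmed, for discharge 2, 3 or 4 days later. Those shares rest on equally likely recovery days and an assumed discharge lag, and are illustrative.

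With a descriptive analysis of 21 subjects this should be corrected, but it does not undermine the trial's safety purpose.

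**What to change.** 1. For the 21 enrolled Part 1 subjects, enter SpO2 and room-air or oxygen status in the eCRF for every inpatient day after Visit 5, retrospectively from the hospital chart, where charted.
2. In SAP 7.2 and 8.2.6, derive the 48-hour run and its start date from these daily values, and flag subjects whose run cannot be confirmed.
3. Reconcile Protocol Sections 5.3, 5.4.2 and 7.2.3.3 on whether SpO2 is a daily record, and amend 5.4.2, Table 2 and SAP Table 1 to match. With enrolment stopped, this amendment alone adds no data.

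The cost is extra chart abstraction, with no new measurement on any patient. The result depends on how completely SpO2 and oxygen status were charted. Where they were not, the report should state that the 48-hour condition could not be verified.

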#### **Day 16**

- Vitals;
- Respiratory assessments per Section 5.3;
- SBT and at any time that weaning criteria is met;
- OSCi assessment;
- AEs;
- Concomitant medications.

#### **Days 18, 21, 24, 28**

- OSCi assessment (Day 28);
- AEs;
- Laboratory (chemistry, hematology, coagulation and urinalysis per Section 5.2) (Day 21 and Day 28 with urinalysis at Day 28)
- Concomitant medications;
- Follow-Up (Telemed) (Day 28).

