**Days 18, 21, 24, 28**

- Laboratory (chemistry, hematology, coagulation per Section 5.2);
- OSCi assessment (Day 28);
- AEs;
- Concomitant medications;
- Follow-Up (Telemed) (Day 28).

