## 7.2 Description of Statistical Methods

### 7.2.1 Analysis of the Efficacy Endpoint(s)

Efficacy assessments will be based on the safety analysis set, which is defined as all subjects who have received at least one dose of study medication. Data relating to efficacy response will be listed and summarized by treatment group and time point, as appropriate. Any efficacy related outcomes in Part 1 will be present descriptively and will be detailed in the SAP.

Summary statistics (mean, median, standard deviation, minimum, and maximum) and change from baseline to each scheduled study assessment for ventilator readings will be presented by treatment group. Baseline is defined as the latest non-missing assessment prior to the first study drug infusion.

The primary efficacy outcome, time to peripheral capillary oxygen saturation ( $\text{SpO}_2$ )  $\geq 94\%$  on room air, sustained for at least 48 hours, through Day 28, will be estimated and compared between the two treatment groups using Kaplan-Meier (KM) analysis. Subjects who do not achieve  $\text{SpO}_2 \geq 94\%$ , sustained for at least 48 hours, or die by Day 28 will be censored at Day 28. As a supplemental analysis, an analysis using a Cox proportional hazards model incorporating the baseline covariates: age, baseline severity, and comorbidity, will be performed.

The secondary efficacy outcome of proportion of subjects with all-cause mortality within 60 days from start of treatment, will be compared between the two treatment groups using Fisher's exact test. In addition, as a supplemental analysis, a logistic regression analysis will also be performed to adjust for the same baseline covariates in the primary efficacy outcome analysis: age, baseline severity, and comorbidity.

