8.2. Primary Outcomes

The primary endpoint of the study will be safety and tolerability, as demonstrated by adverse events (AE), changes in laboratory assessments, ECG assessments, vital signs, and concomitant medications (inotropes and vasopressors). These outcomes will be summarized by cohort. See details in sections 8.2.1 to 8.2.6.

Co-primary endpoint is the difference between USB002 and placebo groups in time to peripheral capillary oxygen saturation (SpO₂) $\geq 94\%$ on room air, sustained for at least 48 hours, through Day 28. All peripheral capillary oxygen saturation (SpO₂) results from baseline to Day 28 will be listed (and summarized if applicable). See section 8.2.7.

No statistical inference will be made for primary endpoint.

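### The primary efficacy window runs to Day 28, but SpO2 is last scheduled on Day 16, so later recoveries are not planned to be observed

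*Protocol*

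**What the plan says.** **The endpoint.** Protocol 2.1.1 defines the primary efficacy endpoint as time to SpO2 of at least 94%, "sustained for at least 48 hours, on room air through Day 28". SAP 4.2 repeats it, and SAP 8.2 calls it co-primary.

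**Where SpO2 is measured.** Protocol 5.3 puts SpO2 under the study-required respiratory assessments. Its own list of daily vitals covers blood pressure, heart rate, respiratory rate and temperature, but not SpO2.

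**When it is measured.** In Protocol 5.4.2 (Part 1), respiratory assessments are listed during the infusion, at Visit 5, on Days 7, 9, 12 and 14, and on Day 16. Under the next heading, "Days 18, 21, 24, 28", the list holds OSCI (Day 28), adverse events, laboratory tests, concomitant medication and the Telemed contact. Protocol 5.4.3 (Part 2) has the same pattern: respiratory assessments on Days 1-14 and Day 16, then for the late visits "Laboratory (chemistry, hematology, coagulation per Section 5.2" with OSCI on Day 28, adverse events, concomitant medication and Telemed. Protocol 5.4.5 gives discharged subjects Telemed contact only.

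**How non-achievers are handled.** Protocol 7.2.1 says that subjects who do not reach the threshold, "sustained for at least 48 hours, or die by Day 28 will be censored at Day 28". The same section says of Part 1: "Any efficacy related outcomes in Part 1 will be present descriptively". SAP 7.2 sets the time to null for a subject who never achieves the threshold and derives the time from the first qualifying date, without the 48-hour condition. SAP 8.2 still expects SpO2 "results from baseline to Day 28 will be listed (and summarized if applicable".

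**The concern.** An endpoint said to run through Day 28 needs measurements that could detect it up to Day 28. Here the scheduled measurements stop 12 days earlier. A subject who comes off oxygen on Day 20 and one who never does would leave the same scheduled SpO2 record.

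Under the protocol rule, both would be counted as event-free to Day 28. Under the SAP rule, both drop out of the summary of times. In either case a result labelled as a 28-day recovery outcome would describe roughly the first two weeks. The inclusion criteria admit subjects ventilated for less than 72 hours, so late recovery is plausible. At stake is what the descriptive result for the 21 Part 1 subjects can claim.

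**Working it through.** The documents give no power, event count or recovery rate for this endpoint, so there is no planned figure to reproduce. The check compares the endpoint window with the schedule and then gauges the size under stated assumptions.

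**1. Last scheduled SpO2**

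| Source | Last listed respiratory assessment | Listed on Days 18, 21, 24, 28? |
|---|---|---|
| Protocol 5.4.2 (Part 1 text) | Day 16 | No |
| Protocol 5.4.3 (Part 2 text) | Day 16 | No |
| Protocol Table 3 (Part 2) | Day 16 (11 marks: Screening, Days 1, 2, 3, 4, 5, 7, 9, 12, 14, 16) | No |

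Protocol Table 2 (Part 1) and the SAP copies of both tables cannot be read reliably by column in the extracted text, so I did not use them. The Part 1 finding rests on the visit text.

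**2. Length of the gap**

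- Days 17-28: 28 - 16 = 12 days; 12/28 = 43% of the window.
- With 48 hours required, the last onset that scheduled visits can confirm is Day 14 (Day 14 to Day 16). That leaves 28 - 14 = 14 days; 14/28 = 50%.
- The first limit fits the SAP 7.2 derivation (no 48-hour condition). The second fits the endpoint as defined in Protocol 2.1.1 and SAP 4.2.

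**3. Share of recoveries in the gap, under an assumed rate**

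Assume exponential recovery with median m, so F(t) = 1 - 2^(-t/m). The share of recoveries due by Day 28 that fall after day t is 1 - F(t)/F(28).

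| m (days, assumed) | F(14) | F(16) | F(28) | After Day 16 | After Day 14 |
|---|---|---|---|---|---|
| 7 | 0.750 | 0.795 | 0.938 | 15% | 20% |
| 10 | 0.621 | 0.670 | 0.856 | 22% | 27% |
| 14 | 0.500 | 0.547 | 0.750 | 27% | 33% |
| 20 | 0.384 | 0.426 | 0.621 | 31% | 38% |

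Setting the rate instead by an assumed Day 28 recovery of 90% down to 30% gives 18.7% to 38.5% after Day 16 and 24.0% to 45.6% after Day 14.

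**4. Leverage of one subject**

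With the planned 3 active and 3 placebo subjects per cohort, one late recovery recorded as none moves that group's proportion by 1/3, or 33 percentage points. In the pooled comparison, if the three full cohorts split 3:3 as planned, each pooled group has between 9 and 12 subjects (the split of the 3 subjects in Cohort 4 is not stated). One subject is then worth 1/12 to 1/9, or 8 to 11 points.

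**The case against.** **No Day 28 censoring in the analysis that will be run.** A reader might infer that non-achievers will be analysed as event-free to Day 28. That rule is in Protocol 7.2.1 only, attached to the two-group Kaplan-Meier comparison. Part 1 efficacy is descriptive, Part 2 was not enrolled (SAP 6.1), SAP 8.2.6 specifies no Kaplan-Meier analysis for this endpoint, and SAP 7.4 rules out inference. This objection stands. The SAP's null has its own cost, however: times are summarised among achievers only, and SAP Section 6 does not list it as a change.

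**Late SpO2 may exist.** A reader might infer that late recoveries cannot be observed, or that any Day 28 listing must be wrong. The documents do not show this. SAP 8.2 plans to list SpO2 to Day 28, SAP 8.2.2 lists all respiratory data, Protocol 7.2.3.3 counts SpO2 among vital signs, Protocol 5.4.3 has a general daily-monitoring sentence for Part 2, and OSCI on Day 28 shows oxygen use. The eCRF is not visible. The supportable wording is that late recoveries are not scheduled to be observed. None of these provisions sets an SpO2 schedule after Day 16 or can date a 48-hour recovery on room air.

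**The size is unknown.** The medians are assumptions. Few subjects, or none, may have been unrecovered and in hospital after Day 16. This also stands.

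**Shortening the window now is a late change.** True. It should therefore be the fallback and be disclosed.

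**Conclusion.** The mismatch is real in both parts. The endpoint runs through Day 28, while the visit text schedules no SpO2 after Day 16, so late recovery and non-recovery can look alike under the plan as written. Onsets after about Day 14 (48-hour definition) or after Day 16 (SAP 7.2 derivation) fall outside scheduled measurement.

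Under exponential recovery with medians of 7 to 20 days, about 15-31% of recoveries due by Day 28 fall after Day 16 and 20-38% after Day 14. These shares rest on that assumption and on no late readings being entered; the number affected among the 21 subjects is unknown.

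The consequence is a descriptive result whose label may exceed its data. No hypothesis test is affected, because none is planned.

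**What to change.** 1. **Preferred.** Where in-hospital SpO2 and room-air status are charted for Days 17-28, enter them and keep the Day 28 window.
2. **Otherwise.** Restate the endpoint in SAP 4.2, 7.2 and 8.2 as observed through Day 16, and list this in SAP Section 6 as a change made after enrolment ended.
3. **In either case:**
   - Report the number of non-achievers, with the last SpO2 date for each, beside the times among achievers.
   - Count deaths as non-recovered to the end of the window. Do not end their follow-up at the last SpO2 record, which would treat them as if they could still recover.
   - Apply the 48-hour condition in the SAP 7.2 derivation, so that it matches SAP 4.2 and 8.2.
4. **Protocol.** Reconcile the assessment schedule and the Day 28 censoring rule in 7.2.1 with the endpoint window.

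The cost is SAP wording plus some chart abstraction for subjects still in hospital after Day 16, or else a shorter stated window decided late and disclosed as such. Hospital charts will not supply readings after discharge, so that part of the gap should be stated as a limitation.
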